#### **4.2.4.2 Adverse events of special interest (AESIs)**

Investigators have been requested to identify the AESIs in reporting. The primary interpretation of data will be made upon those events with investigator assessment. In addition, a supplementary analysis is conducted which runs the narrow Standardised MedDRA Queries (SMQs) for hypersensitivity, the narrow and broad SMQS for anaphylactic reactions, and a study specific query based on compatible PTs for thrombocytopenia and immune complex disease occurring in the database. Narrow hypersensitivity SMQs include some PTs of immune complex disease. These SMQs and PTs will be provided by the medical monitor in a separate document before DBL of each analysis.

See Section [3.1.2](#) for definition of AESIs.

The number and percentage of subjects with treatment-emergent AESIs, as well as categorization by MedDRA SOC and PT and the total number of AESIs will be provided.

The number and percentage of subjects with treatment-emergent AESIs, as well as categorization by MedDRA SOC and PT, and the highest severity will also be provided.

Key information similar to those mentioned in the TEAE section will be listed for subjects with AESIs.

#### **4.2.4.3 Skin reactions and skin hypersensitivity reactions**

The incidence of treatment-emergent skin reactions, skin hypersensitivity reactions and the relationship to IP will be summarized by MedDRA SOC and PT, and the total number of skin reactions and skin hypersensitivity reactions will also be provided. A listing of subjects with skin reactions will also be provided.

The number and percentage of subjects with treatment-emergent skin reactions, as well as categorization by MedDRA SOC and PT, and the highest severity will also be provided.

The number and percentage of subjects with a hypersensitivity/allergic reaction, skin reaction etiology, types of skin reaction, skin reaction distribution, location of skin reaction, history of recent viral illness, the accompanied systemic symptoms and types of drugs exposure to within 14 days of the onset of skin reaction symptoms, as reported on the dedicated eCRF page, will be provided.

#### **4.2.4.4 New onset chronic diseases (NOCDs)**

New onset chronic diseases will be assessed and identified by the Investigator and recorded in the eCRF. The analysis of NOCD will be performed on AEs which have ‘yes’ selected for “NOCD” in the ‘Adverse Events’ eCRF page.

The number and percentage of subjects that are defined as NOCD, as well as categorization by MedDRA SOC and PT, and the total number of NOCD will be provided. Key information similar to those mentioned in the TEAE section will be listed for subjects with TEAEs that are defined as NOCDs.

#### **4.2.4.5 Subgroup analyses**

The following subgroup analysis will be performed on the primary analyses.

##### **Subgroups by AE onset time relative to dosing**

All AE start dates relative to administration date of nirsevimab will be calculated according to study day defined in Section 4.1.3. The categories for this subgroup are:

- ‘within 1 day’ of administration of nirsevimab; defined as study day  $\leq 1$ .
- ‘within 3 days’ of administration of nirsevimab; defined as study day  $\leq 3$ .
- ‘within 7 days’ of administration of nirsevimab; defined as study day  $\leq 7$ .
- ‘within 14 days’ of administration of nirsevimab; defined as study day  $\leq 14$ .

The primary analyses described in the above sections will be repeated for this subgroup analysis.

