#### **4.1.3 Derivation of study day**

Study day will be calculated as follows:

- If the evaluation date is on or after the administration date of nirsevimab:

study day = date of evaluation – administration date of nirsevimab + 1

- If the evaluation date is before the administration date of nirsevimab:  
study day = date of evaluation – administration date of nirsevimab

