##### **4.1.4.2 Imputation rule for partial AE start date**

- When AE range is available:

Step 1: For partial AE start dates, regardless if only the year is known, or only the month and year are known, first use the following rule to impute AE start date:

- a. Assume (dose date + 1 day) if AE started  $\leq$  7 days after dosing;
- b. Assume (dose date + 7 days) if AE started 8 - 14 days after dosing;
- c. Assume (dose date + 14 days) if AE started  $>14$  days after dosing.

Step 2: After getting an imputed AE start date from Step 1, compare the imputed AE start date with the partial AE start date:

- If partial AE start date where only the year is known:
  - If the year of partial AE start date is the same as imputed AE start date from Step 1, then use imputed AE start date from Step 1;
  - If the year of partial AE start date is different from the year of imputed AE start date from Step 1, assume partial AE start date as January 1st;
  - If the imputed AE start date is after AE end date, then set AE start date the same as AE end date.
- If partial AE start date where only the year and month are known:
  - If the year and month of partial AE start date are the same as imputed AE start date from Step 1, then use imputed AE start date from Step 1;
  - Otherwise, assume partial AE start date as the first day of the month.
  - If the imputed AE start date is after AE end date, then set AE start date the same as AE end date.
- When AE range is not available:
  - If partial AE start date where only the year is known,
    - If the same year as dosing date:

- i. If AE does not occur on the same day of dosing, then AE start date is one day after dosing date;
- ii. Otherwise, AE start date is the same as dosing date.
- If different year from dosing date, assume January 1st.
- If partial AE start date where only the year and month are known,
  - If the same year and month as dosing date:
    - i. If AE does not occur on the same day of dosing, then AE start date is one day after dosing date;
    - ii. Otherwise, AE start date is the same as dosing date.
  - Otherwise, assume the first day of that month.

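### The imputation rule for partial AE start dates moves dosing-day events to study day 2 and, after month-end or year-end dosing, to a date before dosing, which removes them from the TEAE summaries; the 'within 1 day' row label needs a minor correction.

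*SAP*

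**What the plan says.** SAP Section 4.1.4.2 has two branches for a partial AE start date.

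- **Range recorded, step 1.** A provisional date is set. Rule (a): "Assume (dose date + 1 day) if AE started" no more than 7 days after dosing. Rule (b): "Assume (dose date + 7 days) if AE started 8 - 14 days after dosing". Rule (c) uses dose date + 14 days for anything later.
- **Range recorded, step 2.** The provisional date stands if it agrees with the known year, or with the known year and month. If it does not, a year-only date becomes 1 January of the recorded year. For a month-and-year date the rule is: "Otherwise, assume partial AE start date as the first day of the month". A result later than the AE end date is pulled back to the end date.
- **No range recorded.** When the known part matches the dosing date: "If AE does not occur on the same day of dosing, then AE start date is one day after dosing date". A dosing-day AE receives the dosing date.

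Under SAP Section 4.1.3, study day from dosing onward is the evaluation date minus the "administration date of nirsevimab + 1". Section 3.1.1 counts an AE as treatment-emergent only if it starts after dosing. Section 4.2.4.1 sends AEs dated before dosing to a listing.

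Section 4.2.4.5 sets four cumulative onset rows, at 1, 3, 7 and 14 days, and ties them to study day: "All AE start dates relative to administration date of nirsevimab will be calculated according to study day defined in Section 4.1.3". Each is labelled as within that many days "of administration of nirsevimab; defined as study day" no greater than the same number. On scope: "The primary analyses described in the above sections will be repeated for this subgroup analysis".

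**The concern.** The three ranges leave only one place for a dosing-day AE: at most 7 days after dosing. Rule (a) then gives it a provisional date one day later than its true onset. This has two consequences.

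First, the AE moves out of the dosing-day row, although the same AE with no recorded range would stay in it. More recorded information gives a less accurate date.

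Second, and more important, step 2 can find that the provisional date lies in the next month or year and reset the start to the beginning of the recorded month or year. The record says the AE followed dosing, yet its imputed start precedes dosing. It then fails the TEAE definition, and the primary safety summaries lose it. By contrast, Section 3.1.1 keeps an AE as treatment-emergent when its onset date is wholly missing and its stop date is after dosing or unknown.

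The labelling point is separate and smaller. A reader may take the first onset row as the first 24 hours, but it holds the dosing date only.

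**Working it through.** **1. Study-day formula (SAP 4.1.3).** On or after dosing, study day = date − dose date + 1. So dose + 0 → 1, + 1 → 2, + 7 → 8, + 14 → 15 and + 360 → 361. The last value reproduces the SAP's own pairing of 360 days post dose with Day 361.

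**2. Three illustrative cases.** Each is a dosing-day AE with month and year known and range at most 7 days.

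- Dose 10 November 2021: step 1(a) gives 11 November, in the recorded month, so it stands. Study day = 11 − 10 + 1 = 2.
- Same dose, with a recorded AE end date of 10 November: 11 November is after the end date, so the start is reset to 10 November, study day 1.
- Dose 30 November 2021: step 1(a) gives 1 December. The recorded month is November, so step 2 gives 1 November. Study day = 1 − 30 = −29, before dosing.

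**3. Every dosing date in 2021.** The AE is a dosing-day AE with range at most 7 days. Entries are numbers of dosing dates.

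| Known part | AE end date | Study day 1 | Study day 2 | Before dosing |
|---|---|---|---|---|
| Month and year | None, or next day | 0 | 353 | 12 |
| Month and year | Dosing day | 353 | 0 | 12 |
| Year only | None, or next day | 0 | 364 | 1 |
| Year only | Dosing day | 364 | 0 | 1 |

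12/365 = 3.3% (the last day of each month) and 1/365 = 0.3% (31 December). The 2022 calendar gives the same counts with no end date forcing a change. A same-day end date rescues the study-day-2 cases but not the pre-dosing ones, because the first of the month or year is not later than the end date.

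**4. Other onsets.** True onsets at dose + 1 to + 7 under rule (a), + 7 to + 14 under rule (b) and + 14 to + 360 under rule (c) give no date before dosing. In those cases the provisional date is never later than the true onset, so any mismatch in step 2 points to a later month or year. Only the dosing-day AE under rule (a) has a provisional date after its true onset.

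**5. First onset row.** Study day ≤ 1 means dose + 0 only, because TEAEs start after dosing. Dose + 1 is study day 2 and first appears in the 3-day row. The documents give no dosing times. For an assumed dose at clock hour h, the row covers 24 − h hours and leaves out h/24 of the first day:

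- 09:00: 15 h covered, 37.5% left out
- 12:00: 12 h covered, 50.0% left out
- 17:00: 7 h covered, 70.8% left out

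**The case against.** The 353 and 12 are counts of calendar dates, weighted equally, and say nothing about how many subjects are affected. The path needs a dosing-day AE, a partial start date and a recorded range; for the loss from the TEAE summaries it also needs month-end or year-end dosing. The eCRF is not among the documents. The no-range branch tests for same-day onset, so that information may be captured separately. All of this stands and limits the size of the problem. It does not make the resulting date right.

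Two stronger readings are tempting, and the documents do not support them.

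- A reader might infer that the onset cut-offs are wrong, or that every row stops a day short. Section 4.2.4.5 defines each row openly. Rules (b) and (c) place their ranges at study days 8 and 15, which agrees with the 7- and 14-day cuts. The pairing of 360 days with Day 361 belongs to the TEAE window and does not govern these rows.
- A reader might infer that immediate hypersensitivity would be missed. Protocol Appendix B describes anaphylaxis as starting within minutes to hours, and at the assumed dosing times the first row still covers 7 to 15 hours, so most such onsets stay in it. The rows are cumulative, AESIs are also summarised and listed with start dates, and no formal comparison is planned. The percentages left out are shares of clock time, not of events.

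**Conclusion.** The imputation fault is real and narrow. With a range of at most 7 days recorded, a dosing-day AE with a partial start date goes to study day 2 unless a same-day end date resets it. After dosing on the last day of a month (12 of 365 dosing dates, month and year known) or on 31 December (1 of 365, year only), it goes to a date before dosing and drops out of the TEAE summaries. This assumes that a dosing-day AE can carry a recorded range. It would be wrong to infer that rule (a) displaces every partial-date dosing-day AE, because AEs with no range and most of those ending on the dosing day keep the dosing date. The number of subjects affected cannot be estimated from the documents and is probably very small.

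The row label is a minor matter of presentation. Apart from the pre-dosing path, overall TEAE, AESI and skin-reaction counts are unaffected. The imputation rule is still worth correcting, because it can remove a true post-dose event from the primary endpoint and the remedy costs almost nothing.

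**What to change.** **SAP 4.1.4.2.**

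- Where a post-dosing range is recorded, do not let step 2 return a start before the dosing date; use the dosing date instead. This alone brings the pre-dosing results from 12 and 1 to 0 and needs no new data.
- Where same-day onset is recorded, keep the dosing date before applying rule (a). In the same enumeration all 365 dosing-day AEs then stay on study day 1. This part depends on the eCRF holding same-day onset alongside the range.
- Leave rules (b) and (c) unchanged.

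**SAP 4.2.4.5.** Keep all four cut-offs and relabel the rows 'day of dosing (Day 1)', 'Days 1-3', 'Days 1-7' and 'Days 1-14'. A 'Days 1-2' row is optional. It would span 24 to 48 hours after dosing and would take in partial-date AEs whose true onset was as late as dose + 7, because rule (a) puts them on study day 2. If the row is added, it should show imputed onsets separately.

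**Cost.** One SAP paragraph, a small derivation edit and new row labels. Early-onset counts may rise slightly where imputed dates are corrected.

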#### **4.2.5 Secondary analyses**

##### **4.2.5.1 Pharmacokinetics**

Nirsevimab serum concentration data for each nominal sampling time will be summarized by dose using descriptive statistics, including  $n <$  lower limit of quantification (LLOQ), geometric mean, geometric coefficient of variation (CV) (%), geometric SD, geometric mean  $\pm$  geometric SD, and the summary statistics listed in Section 4.1.1, and a listing of nirsevimab serum concentrations will also be provided. Line plot of geometric mean of nirsevimab serum concentration on log-normal scale will be plotted by scheduled visit. Geometric mean and other summary statistics are derived from planned visit day  $\pm$  14 days.

Nirsevimab serum concentration at each scheduled visit will be summarized by subject disease conditions as defined in inclusion criterion number 2, see [Appendix 4](#). The summary statistics of number of subjects, mean, SD, minimum and maximum will be provided. A series of spaghetti plots, will be created for each of the disease conditions stated in inclusion criterion number 2, presenting individual subjects nirsevimab serum concentration over time.

Individual nirsevimab serum concentrations with geometric mean  $\pm$  geometric SD will be graphically illustrated, and summarized, by ADA status (ADA positive and ADA negative). Definitions of ADA status are described in Section 0.

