^d Nasal samples will be collected for all LRTIs (inpatient or outpatient) and all subjects hospitalized with any respiratory infection (upper or lower) within 2 days after the diagnosis by a healthcare provider. Blood samples will be collected from all subjects hospitalized with LRTI or any respiratory infection within 2 days following hospital admission.

^e Skin reaction assessment will be done for any post-dosing skin or skin-related reaction regardless of severity, duration, time of onset post dosing, or relationship to investigational product.

^f Telephone contact must be verbal communication. Written communication via text, email, or other written form is not acceptable.

^g HRU includes admission and duration of hospital and ICU stay, number of subjects who require respiratory support and supplemental oxygen use, duration of respiratory support and supplemental oxygen use, number and type of outpatient visits (eg, ER, urgent care, outpatient clinic), and number and days of prescription and OTC medication.

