### 4.1 General principles

There are 2 planned analyses for this study: an interim analysis and a final analysis. The interim analysis will be conducted when subjects enrolled globally by the end of 2021 have been followed through Day 151. The final analysis will be conducted when all subjects have completed the last visit of the study (Day 361). The data will be validated as defined in the Data Management Plan.

- For the visit-based summaries for PK/ADA, CCI and clinical laboratory data, the summaries will be based on the scheduled visits using adjusted analysis-defined visit windows. The adjusted analysis-defined windows will be based on the collection schedule listed in the CSP and summaries will be windowed to the closest scheduled visit for those data. Visit windows have been constructed so that every observation collected can be allocated to a particular visit. All data will be included in the listings. If multiple readings are recorded within a single analysis-defined visit window, the following rules will apply: If there are 2 or more valid, non-missing observations within the same visit window, and
  - if they are on different days, then the non-missing one which is closest to the scheduled visit day will be used in the analysis.
  - if they are on the same day which is closest to the scheduled visit day, then the non-missing one with the later collection time will be used in the analysis.
- If 2 or more valid observations are equidistant from the scheduled visit, and
  - if they are on different days, then the non-missing post-dose observation with the earlier collection date will be used in the analysis for the post-baseline observations, and the non-missing pre-dose observation with the later collection date will be used in the analysis for the screening observations.
  - if they are on the same day, then the non-missing observation with the later collection time will be used in the analysis.
- For LRTI visits or unscheduled visits, if 2 or more valid observations are collected on the same day, then the non-missing observation with the later collection time will be included in the analysis.
- If a visit window does not contain any observations, then the data will remain missing.
- For the visit-based summaries for ADA, if both ADA positive and negative samples are available within a subject's visit, ADA positive will be reported.

- For summary Statistics of PK data following rules apply:

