#### **4.1.1 General data reporting conventions**

Categorical data will be summarized by the number and percentage of subjects in each category. Percentages will be rounded to 1 decimal place. Continuous variables will be summarized by mean, median, standard deviation (SD), minimum, and maximum, unless stated otherwise. The mean and median will be presented with one more decimal place than the raw data. The standard deviation will be presented with two more decimal places than the raw data. Minimum and maximum values will have the same number of decimal places as the raw data.

Data collected at unscheduled visits will not be included in summaries by timepoint or visit unless stated otherwise. Data collected at unscheduled visits will be presented in listings.

In tables and listings, treatment group will be presented as ‘nirsevimab’.

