#### **4.1.7 Reporting PK concentration**

Individual compound concentrations below the lower limit of Quantification (LLOQ) of the assay are reported as NQ (not quantifiable) with the LLOQ defined in the Tables, Figures and Listings (TFLs).

For descriptive statistics:

- If, at a given time point, 50% or less of the plasma concentrations are not quantifiable (NQ), the geomean, coefficient of variation (CV), geoSD, arithmetic mean and standard deviation (SD) are calculated by substituting the limit of quantification (LOQ) for values which are NQ.
- If more than 50%, but not all, of the concentrations are NQ, the geomean, CV, geoSD, arithmetic mean, and SD are reported as not calculable (NC). The max value is reported from the individual data, and the min and median are set to NQ.
- If all the concentrations are NQ, the geomean and arithmetic mean are reported as NQ and the CV, geoSD and SD as NC.
- The number of values below LLOQ are reported for each time point along with the total number of collected values.

Three observations >LLOQ are required as a minimum for a plasma concentration to be summarized. Two values are presented as a minimum and maximum with the other summary statistics as NC.

For consistency, the same plasma concentration values are used in the mean data graphs as those given in the descriptive statistics summary table for each time point.

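### Do the ±14-day rule in SAP 4.2.5.1 and the wide Appendix 2 windows leave the PK summaries with two definitions of Day 151?

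*SAP*

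**What the plan says.** SAP 4.1 bases visit-level PK summaries on analysis windows and explains their coverage: "Visit windows have been constructed so that every observation collected can be allocated to a particular visit". Appendix 2 sets them. For Day 151 the window is Days 92 to 255, for Global and Japan alike. Where a child has several samples in one window, the one closest to the scheduled day is used.

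SAP 4.2.5.1 opens with the by-dose summaries and the line plot. That paragraph closes with: "Geometric mean and other summary statistics are derived from planned visit day" ± 14 days. Two further summaries follow in the same section. One is by condition: "Nirsevimab serum concentration at each scheduled visit will be summarized by subject disease conditions as defined in inclusion criterion number 2". In the other, individual concentrations with the geometric mean are to be "graphically illustrated, and summarized, by ADA status (ADA positive and ADA negative"). Neither repeats or cites the ±14-day limit.

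On extra samples, Protocol Table 5 (footnote d) states: "Blood samples will be collected from all subjects hospitalized with LRTI or any respiratory infection within 2 days following hospital admission". SAP 4.1.1 says: "Data collected at unscheduled visits will not be included in summaries by timepoint or visit unless stated otherwise". SAP 4.1 also has a bullet that begins "For LRTI visits or unscheduled visits, if 2 or more valid observations are collected on the same day", under which the later observation is the one carried into the analysis.

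**The concern.** Two widths are attached to the same visit, 164 days and 29 days, and no text ranks them. The ±14-day sentence closes the by-dose paragraph, so a programmer could apply it there and use the wide windows for the condition and ADA-status tables. The Day 151 rows of different tables would then rest on different samples.

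The protocol makes off-schedule blood foreseeable, because a sample is drawn at any respiratory hospitalization during follow-up. SAP 4.1 and 4.1.1 do not say in one place whether such samples enter by-visit summaries.

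At stake is the descriptive check in Protocol 4.8.4 that adequate exposure lasts at least 5 months. A sample taken well before Day 151 would flatter that row and a late one would depress it. The condition and ADA-positive groups may be small enough for one sample to show.

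**Working it through.** **Reproducing the window.** Assign each study day to the nearest scheduled post-dose PK day (31, 151 or 361). The midpoints are (31 + 151)/2 = 91 and (151 + 361)/2 = 256. The days strictly closest to Day 151 are 92 to 255, as in Appendix 2. The width is 255 - 92 + 1 = 164 days. Under ±14 it is 165 - 137 + 1 = 29 days.

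**Can ±14 stand alone?** No. For Japan, Day 8 + 14 = 22 and Day 31 - 14 = 17, so Days 17 to 22 would belong to two visits. The ±14 rule therefore needs Appendix 2 to allocate first. The two rules do different jobs: one places a sample, the other decides whether it enters the statistics.

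**Which samples differ?** Protocol Table 5 plans Day 151 at ±7 days, that is Days 144 to 158, inside both limits. A sample is treated differently only if it falls on Days 92 to 136 or 166 to 255 and the child has none closer. Protocol Table 7 plans blood at baseline and Days 31, 151 and 361 only, so samples near the window edges would come from hospitalizations or badly displaced visits.

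**Size per sample.** Inputs: half-life 59.3 days (Protocol 1.4.3, Phase 2b) and 72.9 days (upper end in the Phase 1b/2a study). Assumptions: mono-exponential decline, and these half-lives apply to immunocompromised children. Level relative to Day 151 = 2^((151 - d)/half-life).

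| Sample day | 59.3 d | 72.9 d |
|---|---|---|
| 92 | 1.99 | 1.75 |
| 120 | 1.44 | 1.34 |
| 137 | 1.18 | 1.14 |
| 165 | 0.85 | 0.87 |
| 200 | 0.56 | 0.63 |
| 255 | 0.30 | 0.37 |

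**Effect of one such sample on a summary** (59.3 days, all others at their Day 151 level):

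- Dose group of about 50, geometric mean: 1.437^(1/50) = +0.7%; 0.564^(1/50) = -1.1%. At the edges, Days 92 and 255: +1.4% and -2.4%.
- Assumed condition group of 10, arithmetic mean: (9 + 1.437)/10 = +4.4%; (9 + 0.564)/10 = -4.4%. At the edges: +9.9% and -7.0%.
- Assumed ADA-positive group of 6 (the Phase 2b rate of 5.6% applied to 100 children), geometric mean: 1.437^(1/6) = +6%; 0.564^(1/6) = -9%.

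**Against sampling error.** With the Phase 2b AUC coefficient of variation of 35% as a proxy, the standard error of a mean is 35/√50 = 5%, 35/√10 = 11% and 35/√6 = 14%. Every shift listed above for groups of 50 and 10, and for the group of 6, is below one standard error. For an arithmetic mean, a Day 92 sample passes one standard error where 0.993/n exceeds 0.35/√n, which is n of about 8 or fewer. A Day 255 sample does so where 0.703/n exceeds 0.35/√n, which is n of about 4 or fewer.

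**Smallest groups.** SAP 4.1.7 states: "Three observations >LLOQ are required as a minimum for a plasma concentration to be summarized". In a group of three, dropping an out-of-window sample leaves two values. The same section then allows only the minimum and maximum, and the mean is not calculable. A tighter rule there removes the mean and does not improve it.

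**The case for a change.** The strongest case for a change is that the text does not fix the scope and two competent programmers could build different tables. The condition table reports a minimum and maximum, and a Day 255 sample at 0.30 times its Day 151 level could set the minimum whatever the group size. Low values matter most for a claim about lasting exposure. SAP 4.2.7.4 also acknowledges visits and samples disrupted by COVID-19.

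Part of this stands: the SAP is silent on the order of the rules, and an extreme could be set by a late sample. The rest is weaker than it looks:

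- The ±14-day sentence carries no restriction to dose tables. It stands in the only PK analysis section, before the other two summaries, and names the statistics they use.
- The 4.1 bullet on LRTI and unscheduled visits is a tie-break for two samples on one day. It is not a rule admitting such samples to visit tables. Section 4.1.1 keeps unscheduled-visit data out by default, although it does not name LRTI visits.
- The ADA-status paragraph does not say that it reports by visit, so a Day 151 row there is itself an inference.
- An odd minimum can be traced. SAP 4.1 puts all data in the listings, and 4.2.5.1 plans individual concentration plots over time for each condition.
- The table specifications are in separate documents not available here and may already settle the order.

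**Conclusion.** This is missing detail that analysts can fill sensibly: allocate by Appendix 2, then keep samples within ±14 days for the statistics. A sentence saying so would be a convenience, but nothing in the results or conclusions depends on it.

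The samples concerned should be few. One Day 120 or Day 200 sample moves a dose-group geometric mean by about 1% and the mean of an assumed group of 10 by about 4%, both within one standard error. Larger relative shifts need a sample at the window edge in a very small group. In groups of three the restriction has its own cost, because the mean is lost. PK concentration is a secondary, descriptive endpoint, SAP Section 4 plans no formal comparisons, and the extrapolation in Protocol 1.5 rests on population PK, which does not use these windows.

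This rests on mono-exponential decline at half-lives from healthy preterm infants, on the AUC coefficient of variation as a proxy for Day 151 variability, and on assumed subgroup sizes, which the documents do not give. The number of off-schedule samples is not known either. If many visits were displaced the question would deserve another look, and the listings would show it.
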